**Secondary outcomes:**

Differences among treatment groups with respect to secondary continuous outcomes (post-operative median length of stay, cost) will be assessed using two-sample t-tests or Wilcoxon rank sum tests. Differences in binary outcomes (readmission rate, post-operative complications, delayed gastric emptying, anastomotic leaks, intra-abdominal abscesses, wound infection, urinary tract infection, respiratory compromise, renal failure) will be assessed using Chi-square tests or Fisher's exact test)

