### 1.1 Specific Aims and Hypothesis

**Hypothesis:** The use of an accelerated pathway will result in a shorter postoperative hospital length of stay for patients undergoing PD without an increase in perioperative complications or readmission rates.

**Primary endpoint:** Post-operative length of stay (proportion of patients discharged by POD 5)

**Secondary endpoints:** Post-operative median length of stay, cost, readmission rate, post-operative complications (DGE, anastomotic leaks, intra-abdominal abscesses, wound infection, UTI, respiratory compromise, renal failure, etc.)

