### **2.2 Secondary Objective:**

We anticipate lower cost, similar readmission rate, similar rate of post-operative complications (DGE, anastomotic leaks, intra-abdominal abscesses, wound infection, UTI, respiratory compromise, renal failure, etc.) in our study group

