**Safety:**

The primary safety outcome is hospital readmission. We will employ a Bayesian safety monitoring rule to stop the study if  $\Pr(\pi_{5day} - \pi_{control} > 0.05) > 0.9$  where  $\pi_{5day}$  is the true rate of hospital readmission under the 5 day protocol and  $\pi_{control}$  is the rate under standard of care. The rule means we will stop the study if there is high posterior probability (greater than 90%) that the readmission rate is 5% higher with the 5 day protocol than under standard of care. Over the last 1000 cases, the rate of readmission under standard care is 15%. We assume prior distributions of  $\pi_{5day} \sim \text{Beta}(0.2, 0.8)$  and  $\pi_{control} \sim \text{Beta}(15, 85)$ . That is, we assume the rate in under the 5 day protocol is higher, but with fairly high uncertainty, and we assume 15% under control equivalent to information from 100 subjects. Posterior probabilities will be calculated at the time of the interim efficacy analysis and every 12 patients thereafter. Stopping rules at the interim analysis (36 patients per group) are shown below:

Readmissions in Standard of Care (out of 36)	Stop if Readmissions in 5 day arm are $\geq$ (out of 36)
1-2	10
3-5	11
6-8	12
9-12	13

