We propose to submit to the DSMC for review all AE/SAE’s specifically related to the WARP protocol interventions. These include, renal injury related to the volume restriction, injury related to enhanced physical therapy such as a fall, intolerance of the intervention (full liquid) diet with dizziness or lightheadedness. Given the fact that more than 50% of all pancreaticoduodenectomy patients develop some postoperative complication, such as pancreatic fistula, delayed gastric emptying, intraabdominal abscess, wound infection, urine infection, heart attacks, arrhythmias, pulmonary complications, renal, strokes, and deep vein thrombosis, and that these bear no relation to the specific interventions of the WARP protocol, they will not be reported to the DSMC.

	Grade 1	Grade 2	Grade 2	Grade 3		Grade 3		Grades 4 and 5
	Unexpected and Expected	Unexpected	Expected	Unexpected with Hospitalization	Unexpected without Hospitalization	Expected with Hospitalization	Expected without Hospitalization	Unexpected and Expected
Unrelated Unlikely	Reviewed at	Reviewed at	Reviewed at	5 Working Days	Reviewed at Quarterly	5 Working Days	Reviewed at Quarterly	Phase 1 - 48 Hours

	Quarterly DSMC Meeting and IRB Annual Review	Quarterly DSMC Meeting and IRB Annual Review	Quarterly DSMC Meeting and IRB Annual Review		DSMC Meeting and IRB Annual Review		DSMC Meeting and IRB Annual Review	(Death: 24 Hours)  Phase 2 - 5 Working Days
Possible Probable Definite	Reviewed at Quarterly DSMC Meeting and IRB Annual Review	5 working days	Reviewed at Quarterly DSMC Meeting and IRB Annual Review	48 Hours (Death: 24 Hours)	Phase 1 - 48 Hours  Phase 2 - 5 Working Days	48 Hours (Death: 24 Hours)	Reviewed at Quarterly DSMC Meeting and IRB Annual Review	Phase 1 and Phase 2 - 48 Hours (Death: 24 Hours)

**\*\*NOTE:** This table is based on the NCI AE/SAE reporting Guidelines and the TJU IRB Policy and Procedures. Please follow the individual protocol AE/SAE reporting guidelines if more stringent reporting procedures are specified.

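### The objective claims shorter stay without more complications or readmissions, but no planned analysis can support that second half

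*Combined protocol and SAP*

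**What the plan says.** Section 1.1 hypothesizes a "shorter postoperative hospital length of stay for patients undergoing PD without an increase in perioperative complications or readmission rates". Section 2.1 and the Study Summary repeat this as the objective. Section 2.2 adds: "We anticipate lower cost, similar readmission rate, similar rate of post-operative complications". Neither the no-increase claim nor the word similar is defined.

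The analysis is in section 7.2. Under Secondary outcomes the text reads "Differences in binary outcomes (readmission rate, post-operative complications, delayed gastric emptying", followed by further complications, all compared by chi-square or Fisher's exact test. Under Safety, readmission also has a Bayesian rule: stop if the posterior probability that the 5-day arm exceeds control by more than 5 points is above 0.9. On timing, "Posterior probabilities will be calculated at the time of the interim efficacy analysis and every 12 patients thereafter".

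Complications have no stopping rule. Section 8.5.1 puts their frequency at "more than 50% of all pancreaticoduodenectomy patients develop some postoperative complication". It then says of the common ones that "these bear no relation to the specific interventions of the WARP protocol, they will not be reported to the DSMC", although the general text of the same section says all AE/SAEs go to that committee.

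The sample size (7.1) rests only on the proportion discharged on POD 5.

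**The concern.** The objective has two parts, and the second is a claim that something did not get worse. A test of difference cannot establish that, because a large p-value is compatible with both no increase and a substantial one. The Bayesian rule is one-directional: crossing its boundary is evidence of harm, but staying below it is not evidence of safety.

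Sections 1.6 and 5.3 name delayed recognition of complications after discharge as a major risk of the research. A positive POD 5 result beside non-significant safety tests would invite the conclusion that the pathway shortens stay safely. Nothing in the plan would show the reader how weak the safety comparison is.

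**Working it through.** **Inputs from the plan.** 71 per arm; interim at 72 patients (36 per arm); efficacy bounds p < 0.00506 and p < 0.04553; POD 5 discharge 10% v 30% (7.1, 7.2). Control readmission 15%; priors Beta(0.2, 0.8) for the 5-day arm and Beta(15, 85) for control (7.2, Safety). Complications above 50% (8.5.1), taken as 50%.

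**Assumptions.** Two-sided 0.05 for secondary tests, since none is stated. Exact 1:1 accrual and complete readmission data at each look, so that looks every 12 patients fall at 36, 42, 48, 54, 60 and 66 per arm.

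**Step 1: reproduce the plan's figures.** Exact enumeration of the two-stage Fisher design gives power 80.3% and early efficacy stopping 16.3% (plan: 80% and 16.2%). Integrating the Beta posteriors at 36 per arm gives stopping counts of 10, 11, 12 and 13, matching every row of the SAP table.

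**Step 2: readmission.** Test power is the sum of binomial probabilities over all 71 v 71 tables with p ≤ 0.05. The rule's stopping probability comes from an exact recursion over the six looks. The last column is the probability that the rule never fires and Fisher at 71 per arm does not show a significant excess.

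| True 5-day rate (control 15%) | Fisher power | Uncorrected chi-square power | Rule stops | Neither signals harm |
|---|---|---|---|---|
| 15% | – | – | 2% | 97% |
| 20% | 8.6% | 12% | 14% | 83% |
| 25% | 25% | 32% | 42% | 55% |
| 30% | 50% | 58.5% | 73% | 25% |

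The 97% counts only Fisher results in the harm direction; counting either direction gives 95.6%.

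Silence on both checks is 0.971/0.833 = 1.17 times as likely under no increase as under a 5-point rise, and 0.971/0.545 = 1.78 times as likely as under a 10-point rise. That is very weak evidence of no increase.

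The trial may also stop early for efficacy. At 36 per arm both checks are silent with probability 0.755 (true 25%) and 0.520 (true 30%). Weighting by the plan's 16.2%, assumed independent of readmission:
- true 25%: 0.162 × 0.755 + 0.838 × 0.545 = 0.579
- true 30%: 0.162 × 0.520 + 0.838 × 0.247 = 0.291

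**Step 3: a concrete result.** Suppose 11/71 control and 19/71 5-day patients are readmitted, a difference of 8/71 = 11.3 points. Fisher p = 0.15. If the rule were applied at 71 per arm, its boundary would be 20, so it would not fire. The standard error is √[(11/71)(60/71)/71 + (19/71)(52/71)/71] = 0.068, so the Wald 95% CI is 11.3 ± 13.3, about −2 to +25 points. As written, the plan commits only to reporting the non-significant test.

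**Step 4: complications.** Fisher power for 50% v 60% is 18% (chi-square 23%). With 36/71 in control, 48/71 in the 5-day arm gives p = 0.060 and 49/71 gives p = 0.040. Significance therefore needs an observed excess of 13/71 = 18 points.

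**Step 5: achievable precision.** The 95% CI half-width is 1.96 × √[2p(1−p)/n].

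| Outcome | 71 per arm | 36 per arm |
|---|---|---|
| Readmission, p = 0.15 | ±11.7 points | ±16.5 points |
| Complications, p = 0.50 | ±16.4 points | ±23.1 points |

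**The case against.** The plan never says that p > 0.05, or an untriggered rule, will be read as no increase. Section 1.1 is a hypothesis and 2.2 only an expectation. Discharge by POD 5 is the sole primary endpoint, and the sample size and alpha attach to it alone, so the statistical hierarchy is largely right already. Intervals can be computed later from arm-level counts. The readmission rule does set a 5-point threshold and a posterior probability. Complications are still tracked to 90 days, and their reporting to the committee is a question of oversight.

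Much of this is fair, and it limits the point to the safety claim and its reporting; the primary test is not in question. But the no-increase wording is in the primary objective itself, and nothing commits the authors to an interval or rules out the wrong reading. The rule is already counted in the readmission figures above, and it does not cover complications. The committee text matters here only because it leaves the test of difference as the sole planned formal comparison for complications.

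The looks are idealized. Readmission data will lag POD 5 data, so the rule's stopping rates are best case and actual escape may be higher. Patients randomized while the interim cohort completes follow-up would narrow the 36-per-arm intervals somewhat. The Study Summary and 4.4 give 138 patients rather than 142; at 69 per arm the readmission half-width is ±11.9 points, so the conclusion is the same.

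Demanding formal non-inferiority instead would not be realistic. At 15% in both arms, one-sided 0.025 and 80% power, assumed margins of 5, 10 and 15 points need 801, 201 and 89 per arm.

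**Conclusion.** The concern holds and should be fixed. The analysis as written cannot support the no-increase half of the primary objective, and the gap is widest for complications. For readmission, true rises of 5 and 10 points pass both checks more often than not, and a doubling passes about one time in four, or 29% after allowing for an early efficacy stop. These figures rest on 71 per arm, two-sided 0.05, 15% control readmission, 50% control complications and idealized looks. The validity of the POD 5 comparison is unaffected.

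**What to change.** - **7.2, Secondary outcomes:** make the final analysis of readmission and of overall complications the risk difference (5-day minus control) with a two-sided 95% CI.
- **7.2, Safety:** also report the final posterior probability that the readmission difference exceeds 0.05. Note that it uses an informative control prior and a very weak 5-day prior, so it may not agree exactly with the CI.
- **1.1, 2.1, 2.2 and the Study Summary:** state discharge by POD 5 as the confirmatory claim and safety outcomes as estimated.
- **Precision:** state about ±12 points for readmission and ±16 for complications at 71 per arm, and about ±16.5 and ±23 if stopped at 36 per arm.
- **Interpretation:** state that absence of an increase, or similarity, will not be concluded from a non-significant test or an untriggered harm rule.
- **8.5.1:** reconcile the two statements on which events reach the committee.

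The cost is wording, two intervals and one posterior probability added to tables already planned. Sample size, primary analysis and stopping rules stay as they are. The downside is a less favourable published safety statement.

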#### **1.6 Dose Rationale and Risk/Benefits**

The major risks for this research are the development of postoperative complications in the outpatient setting, where identification of these complications may be delayed. The risk of fall due to early mobilization with physical therapy, and the potential for dehydration if patients are not able to tolerate adequate oral intake to maintain hydration at home following discharge. Specific measures to minimize these risks are detailed in the next question. Additional risks include violation of loss of confidentiality or violations in protecting personal health information.

The risk of a delayed diagnosis of postoperative complications will be mitigated with increased outpatient communication including daily phone calls and liberalized use of visiting nursing services and outpatient physical therapy. The risk of falls due to early mobilization will be mitigated by having physical therapy

and/or occupational therapy staff present at all additional therapy sessions beyond our current 7 day standard. The risk of dehydration will be mitigated by frequent daily phone contact by a highly-qualified nurse practitioner in the postoperative outpatient setting. Standard protocols as detailed above will be in place to protect patient PHI.

Patients in the study will benefit from increased and standardized physical and occupational therapy services in the postoperative setting, potential for improved pain control through the use of multimodal therapy, and increased preoperative and postoperative outpatient support by a highly-qualified service-specific nurse practitioner.

Decreased length of hospital stay and increased support (as detailed above) may prove to reduce the rate of overall complications and will allow patients return home quicker. Additional benefit may come in the form of reduced overall cost of care.

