#### **5.3 Risks**

The major risks for this research are the development of postoperative complications in the outpatient setting, where identification of these complications may be delayed. Other risks to these patients that are not present in our

standard 7 day discharge patient includes the the risk of fall due to early mobilization with physical therapy, and the potential for dehydration if patients are not able to tolerate adequate oral intake to maintain hydration at home following discharge. Specific measures to minimize these risks are detailed in the next question. Additional risks include violation of loss of confidentiality or violations in protecting personal health information.

The risk of a delayed diagnosis of postoperative complications will be mitigated with increased outpatient communication including daily phone calls and liberalized use of visiting nursing services and outpatient physical therapy. The risk of falls due to early mobilization will be mitigated by having physical therapy and/or occupational therapy staff present at all additional therapy sessions beyond our current 7 day standard. The risk of dehydration will be mitigated by frequent daily phone contact by a highly-qualified nurse practitioner in the postoperative outpatient setting. Standard protocols as detailed above will be in place to protect patient PHI.

Patients in the study will benefit from increased and standardized physical and occupational therapy services in the postoperative setting, potential for improved pain control through the use of multimodal therapy, and increased preoperative and postoperative outpatient support by a highly-qualified service-specific nurse practitioner.

Decreased length of hospital stay and increased support (as detailed above) may prove to reduce the rate of overall complications and will allow patients return home quicker. Additional benefit may come in the form of reduced overall cost of care.

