## 8.0 SAFETY AND ADVERSE EVENTS

### 8.1 Definitions

#### ***Adverse Event***

An ***adverse event*** (AE) is any symptom, sign, illness or experience that develops or worsens in severity during the course of the study. Intercurrent illnesses or injuries should be regarded as adverse events. Abnormal results of diagnostic procedures are considered to be adverse events if the abnormality:

- results in study withdrawal
- is associated with a serious adverse event
- is associated with clinical signs or symptoms
- leads to additional treatment or to further diagnostic tests
- is considered by the investigator to be of clinical significance

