#### ***Adverse Event Reporting Period***

The study period during which adverse events must be reported is normally defined as the period from the initiation of any study procedures to the end

of the study treatment follow-up. Adverse event reporting will continue until 90 days following their operation or the end of their index hospitalization (whichever is longer).

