### ***Hospitalization, Prolonged Hospitalization or Surgery***

Any adverse event that results in hospitalization or prolonged hospitalization should be documented and reported as a serious adverse event unless specifically instructed otherwise in this protocol. Any condition responsible for surgery should be documented as an adverse event if the condition meets the criteria for and adverse event.

Neither the condition, hospitalization, prolonged hospitalization, nor surgery are reported as an adverse event in the following circumstances:

- Hospitalization or prolonged hospitalization for diagnostic or elective surgical procedures for a preexisting condition. Surgery should **not** be reported as an outcome of an adverse event if the purpose of the surgery was elective or diagnostic and the outcome was uneventful.

- Hospitalization or prolonged hospitalization required to allow efficacy measurement for the study.
- Hospitalization or prolonged hospitalization for therapy of the target disease of the study, unless it is a worsening or increase in frequency of hospital admissions as judged by the clinical investigator.

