## **8.2 Recording of Adverse Events**

At each contact with the subject, the investigator must seek information on adverse events by specific questioning and, as appropriate, by examination. Information on all adverse events should be recorded immediately in the source document, and also in the appropriate adverse event module of the case report form (CRF). All clearly related signs, symptoms, and abnormal diagnostic procedures results should be recorded in the source document, though should be grouped under one diagnosis.

All adverse events occurring during the study period must be recorded if related to the study interventions.

The clinical course of each event should be followed until resolution, stabilization, or until it has been determined that the study treatment or participation is not the cause. Serious adverse events that are still ongoing at the end of the study period must be followed up to determine the final outcome. Any serious adverse event that occurs after the study period and is considered to be possibly related to the study interventions should be recorded and reported immediately.

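### Falls and dehydration, named as added risks of the 5-day pathway, get no by-arm result of their own, and the narrower adverse-event wording could leave milder control-arm events unlogged

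*Combined protocol and SAP*

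**What the plan says.** **Named harms.** Section 1.6 lists among the risks of the research "The risk of fall due to early mobilization with physical therapy, and the potential for dehydration" when oral intake at home is poor. Section 5.3 presents the same two as risks not found in the "standard 7 day discharge patient includes the the risk of fall due to early mobilization with physical therapy", followed by dehydration.

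**Outcomes compared by arm.** Section 7.2 tests nine binary items: readmission, post-operative complications, delayed gastric emptying, and then "anastomotic leaks, intra-abdominal abscesses, wound infection, urinary tract infection, respiratory compromise, renal failure) will be assessed using Chi-square tests" or Fisher's exact test. Neither falls nor dehydration has a line. The primary safety outcome and its Bayesian stopping rule use readmission alone.

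**Recording, general text.** Section 8.1 defines an adverse event as "any symptom, sign, illness or experience that develops or worsens in severity during the course of the study". On the window it says: "Adverse event reporting will continue until 90 days following their operation", or to the end of the index stay if that is later. On hospitalization: "Any adverse event that results in hospitalization or prolonged hospitalization should be documented and reported as a serious adverse event", subject to listed exceptions. Section 8.2 opens in the same spirit: "Information on all adverse events should be recorded immediately in the source document". None of this depends on arm or relatedness.

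**Recording, study-specific text.** Later in 8.2: "All adverse events occurring during the study period must be recorded if related to the study interventions". Section 8.5.1 then describes real-time tracking of events related to the study interventions. It proposes to send the DSMC only those tied to the WARP interventions: renal injury from volume restriction, injury from the enhanced physical therapy such as a fall, and intolerance of the intervention diet with dizziness or lightheadedness. Dehydration is not named there.

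**The concern.** The primary objective (2.1) is a shorter stay with no rise in complications or readmissions. A reader will want to know whether the two harms that the protocol itself attributes to the pathway were more frequent in the 5-day arm. The plan does not ensure an answer.

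The recording rule adds to this. Control patients are not assigned the enhanced therapy or the modified diet, and the trial is unblinded, so a control-arm fall or episode of dehydration can hardly be judged related to either. Where the relatedness wording governs, the two arms are counted by different rules. An apparent excess in the 5-day arm could then be a pathway effect or only fuller logging, and the DSMC would have no control count to set against it.

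**Working it through.** The plan gives no rate for falls or dehydration, so it has no figure of its own to reproduce. The check has four steps.

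**1. The provisions side by side**

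| Place | Limited to related events? |
|---|---|
| Summary schema: complications collected after randomisation | No |
| 3.4: complications, morbidity, mortality, readmission tracked | No |
| 8.1: definition, 90-day window, hospitalization rule | No |
| 8.2, opening | No |
| 8.5.1: general reporting text, and the table row for unrelated or unlikely events | No |
| 8.2, later sentence on what must be recorded | Yes |
| 8.5.1: tracking by attending physicians | Yes |
| 8.5.1: study-specific DSMC list | Yes |

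The general text points to both arms. The sentences written for this trial point to intervention-related events.

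**2. Effect of unequal logging.** Inputs: 71 per arm (7.1); the same true rate p in both arms, all 5-day events logged and a fraction c of control events logged (all three assumed). Mean false excess = p − cp = p(1 − c). For example, 0.10 × (1 − 0.5) = 0.05, or 5 points. With X ~ Bin(71, p) and Y ~ Bin(71, cp), exact enumeration gives the chance that the 5-day arm shows at least 4 more events (4/71 = 5.6 points). Each cell shows mean false excess in points; chance of at least 4 more.

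| True rate | c = 100% | c = 90% | c = 75% | c = 50% |
|---|---|---|---|---|
| 1% | 0; 0.3% | 0.1; 0.3% | 0.25; 0.4% | 0.5; 0.4% |
| 2% | 0; 1.9% | 0.2; 2.1% | 0.5; 2.4% | 1.0; 3.2% |
| 5% | 0; 9% | 0.5; 10% | 1.25; 14% | 2.5; 22% |
| 10% | 0; 16% | 1.0; 21% | 2.5; 30% | 5.0; 50% |

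**3. Can the existing outcomes stand in?** Section 8.5.1 puts overall complications above 50%. Take a 50% background and an assumed harm of 0% v 10%. If the two are independent, the overall item becomes 1 − 0.5 × 0.9 = 55%, a shift of 5 points; with full overlap the shift is 0, with none it is 10. For readmission, take the stated 15% and assume that half of a 10% dehydration rate is readmitted: 1 − 0.85 × 0.95 = 19.25%, so about 19% v 15%, and the other half is not seen there.

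**4. Precision of a by-arm table.** Exact unconditional 95% intervals for the risk difference, 71 per arm (score statistic inverted, maximised over the nuisance rate):

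| 5-day v control events | Difference (95% CI), points |
|---|---|
| 0 v 0 | 0 (−5.3 to 5.3) |
| 4 v 4 | 0 (−8.9 to 8.9) |
| 7 v 4 | 4.2 (−5.4 to 14.3) |

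The last row is close to what p = 10% and c = 50% would produce with no true difference (71 × 0.10 = 7.1; 71 × 0.05 = 3.6). A significance test would add little: two-sided Fisher power at 0.05 is about 12% for 5% v 10% and 41% for 5% v 15%.

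**The case against.** The best reply is that the plan already covers both arms. Section 3.4 and the schema track complications with no arm or relatedness limit; 8.5.1 keeps logs for each patient and has the Medical Monitor review non-reportable events and other safety data; the complication lists in sections 1.1, 2.0, 2.2 and 3.3 are open-ended. The later sentence in 8.2 does not say that only related events are recorded, so it can be read as a firm minimum beneath a general instruction. The DSMC list limits what is submitted, not what is captured: common complications are withheld from the DSMC yet compared by arm in 7.2. Serious cases are also partly caught: dehydration that brings a patient back is a readmission, renal failure has its own comparison, and a fall that causes or prolongs hospitalization falls under the serious-event rule in either arm.

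Most of this stands. A reader might infer that control-arm falls and dehydration will not be recorded, or that the safety comparison as a whole is biased. The documents do not support either inference.

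What remains is narrower. Open-ended lists and the undefined complications item do not give these two harms a result of their own. The per-patient log in 8.5.1 is still described as one of study-intervention events. And the text does not say which recording rule prevails for milder events.

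**Conclusion.** The point holds as a low-cost improvement. That 7.2 has no by-arm line for falls or dehydration is plain from the text. That control-arm events might be under-logged is conditional on staff following the narrower sentences, and concerns mainly milder events. It affects neither the primary analysis nor the readmission stopping rule.

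The size is uncertain because every event rate and logging fraction is assumed. It runs from negligible at a true rate of 1–2% (with half of control events logged, the chance of at least 4 excess events rises only from 0.3% to 0.4%, or from 1.9% to 3.2%) to an average false excess of 5 points at a 10% rate with half of control events logged.

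Nor should a reader expect the remedy to give an unbiased estimate. Assessors remain unblinded, and sections 1.3 and 5.1 list the post-discharge nurse calls under the intervention arm, while the schema and 5.6 do not limit them by arm. If the calls are made only in the 5-day arm, some difference in ascertainment persists.

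**What to change.** - **8.2 and 8.5.1:** drop the relatedness condition for two event types, (1) any fall and (2) dehydration or poor oral intake with dizziness or lightheadedness. Define both without reference to arm, therapy or diet. Record them in both arms to 90 days after operation from the existing complication cards and chart review, noting the source of each event so that those found only through nurse calls can be identified.
- **7.2:** report counts and risk differences by randomised arm with exact 95% confidence intervals, descriptively and without a test. State whether these events count towards the post-operative complications item.
- **DSMC:** supply the same two-arm table at each quarterly review.
- **3.1:** state the 90-day window for these events, since this section ends participation at the first postoperative visit.

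The cost is a short wording change and some control-arm chart review. No patients are added and alpha is unaffected.
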